5 STUDY POPULATION

It is anticipated that this study will enroll a total of approximately 220 subjects. This includes 140 children in the vaccination cohort [20 children between 6-12 months, 60 children with a birth date after 2009 (35 children <3 years of age and 25 children \geq 3 years of age), 30 children with a birth date between 2006 and 2009, and 30 children with a birth date between 2003 and 2006]. We also will enroll up to 80 children total who present with acute influenza infection (20 children into each of the 4 age cohorts). We anticipate having to screen up to 500 children presenting with signs of ILI during the height of seasonal influenza circulation in order to identify and recruit these 80 children with natural influenza infection, as only a small number of children with symptoms possibly consistent with influenza will actually have respiratory infections as a result of influenza virus infection. It is anticipated approximately two-thirds of the children in all cohorts (both A and B) will enroll in the optional year of longitudinal follow-up.

The goal of this study is to understand the development of influenza-specific immunity in a population of children in the Rochester, NY area. Children will be excluded from participation in the study if they meet exclusion criteria of the protocol such as having a documented immunodeficiency or are on immunosuppressive medications expected to have a more than a minimal impact on the development of an immune response to vaccination or infection. Other conditions that may possibly have more than a minimal effect a child's immune system, such as allergies or other hypersensitivity syndromes, mild asthma, or obesity, will be able to enroll in the study. The presence or absence of concomitant medications and medical conditions will be documented and the effect of potential confounding variables will be examined in data analysis.

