11.4 Final Analysis Plan

Data will be analyzed at the end of the study, with results available for publication at that time.

A cohort of n=20 to 60 healthy children that receive a prime-boost vaccination with IIV and n=20 children infected with influenza acutely will be recruited for each age cohort. Their T cell and antibody responses will be measured at three time points: baseline, day 8, and day 24 post-vaccination. We will apply Shapiro-Wilk's test to check the normality. If the data passes the normality test, two sample *t*-tests will be used to detect significant mean difference between the children of different ages and flu exposures at each time point. Otherwise, Wilcoxon rank-sum test will be used. For follow up visits, subjects will be followed longitudinally for one to two years with yearly revaccination with IIV. CD4 T cell responses (flow cytometry) and B cell and antibody responses will be measured at three time points: prior to IIV re-vaccination, 8 and 24 days post re-vaccination. We will apply one-way ANOVA *F*-test (or Kruskal-Wallis test, if the

normality assumption is rejected) to detect significant group differences at each time point. Because multiple response variables are used in this analysis, the p -values will be adjusted by the Benjamini-Hochberg multiple testing procedure [38] to control the false discovery rate (FDR) at the level of 0.05.

General linear models of difference or fold change in T/B cell response at following time points from baseline will be used to explore how childhood exposures affect immune responses over time, while controlling potentially confounding variables including age, sex, presence of asthma or allergies, or other acute or chronic illnesses and medications that may impact the immune response. In addition to time-specific comparisons, the following linear mixed effect model will be used to analyze data collected from all time points

$$y_{kit} = \alpha_k + \beta_{1k}G(i) + \beta_{2k}X_{kit} + \gamma_{kt} + \dot{\mathbf{0}}_{kit}. \quad (0.1)$$

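### Section 11.4 lets a normality pretest pick the test and leaves unequal variances unaddressed: at 60 v 20 children the false-positive rate could lie anywhere from about 1% to 15%

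*Combined protocol and SAP*

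**What the plan says.** Section 11.4 starts from a distributional check: "We will apply Shapiro-Wilk's test to check the normality". It continues "If the data passes the normality test, two sample" *t*-tests, aimed at a "significant mean difference between the children of different ages and flu exposures at each time point". The fallback is "Otherwise, Wilcoxon rank-sum test will be used".

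For the revaccination seasons, "We will apply one-way ANOVA" or, with Kruskal-Wallis as the alternative, the choice again depends on whether the "normality assumption is rejected) to detect significant group differences at each time point". P-values across response variables then go through the Benjamini-Hochberg "multiple testing procedure [38] to control the false discovery rate (FDR) at the level of 0.05".

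The section does not give the level of the pretest, the data it is run on (each group, pooled data or residuals), the scale (raw or log), the version of the t-test, or the groups entering the ANOVA.

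Section 5 plans 20, 60, 30 and 30 vaccinated children in age cohorts 1 to 4, and for infection "20 children into each of the 4 age cohorts". Section 11.2 says that the variability of many measurements is not known.

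**The concern.** A Shapiro-Wilk test says nothing about whether two groups have the same spread. With unequal group sizes, the pooled t-test and the usual F-test depend on equal spread. If the smaller group is the more variable, they reject too often; if the larger group is, they reject too seldom and lose power. The rank test moves in the same direction and is no safe harbour.

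Equal spread cannot be taken for granted here. Infected children may differ in infecting virus, time since onset and prior vaccination, whereas vaccinated children in cohorts 2 to 4 must have completed primary vaccination. Whether this makes the infected groups more variable is not something the documents show.

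The second issue is consistency. The outcome of a pretest varies with sample size and with chance. If it is run by visit, one CD4 or antibody response could be tested on means at day 8 and on ranks at day 24. That makes the results hard to read together in a study with durability among its objectives (Section 3.1). Section 11.3 also allows assay results to be reviewed as they arrive, so it matters that the test is fixed beforehand.

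**Working it through.** The plan states no power or type I error calculation, so there is no figure of its own to reproduce.

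**Inputs.** Group sizes: Section 5. FDR level: Section 11.4. Assumed, because the documents are silent: two-sided 0.05 per test; Shapiro-Wilk at 0.05 in each group; pooled t-test if both groups pass, otherwise Wilcoxon; ratio *r* of the SD in the 20-child infected group to the SD in the vaccinated group, from 0.5 to 2.

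**Step 1: large-sample arithmetic for the pooled t-test.** With SDs 1 and *r*, the expected pooled variance is

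s² = [(n₁ − 1) + (n₂ − 1)r²] / (n₁ + n₂ − 2).

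The test uses V = s²(1/n₁ + 1/n₂), while the true variance of the difference is T = 1/n₁ + r²/n₂. The false-positive rate is about 2Φ(−1.96√(V/T)).

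- 60 v 20, r = 2: s² = (59 + 76)/78 = 1.731; V = 0.1154; T = 0.2167; √(V/T) = 0.730; rate 2Φ(−1.43) ≈ 15%.
- 60 v 20, r = 0.5: s² = (59 + 4.75)/78 = 0.817; V = 0.0545; T = 0.0292; √(V/T) = 1.367; rate 2Φ(−2.68) ≈ 0.7%.
- 30 v 20, r = 2: s² = (29 + 76)/48 = 2.188; V = 0.1823; T = 0.2333; √(V/T) = 0.884; rate 2Φ(−1.73) ≈ 8%.
- 30 v 20, r = 0.5: s² = (29 + 4.75)/48 = 0.703; V = 0.0586; T = 0.0458; √(V/T) = 1.131; rate 2Φ(−2.22) ≈ 2.7%.
- 20 v 20: V = T for every r, so the rate stays near 5%.

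**Step 2: simulation of the whole two-stage rule.** Normal data, true null, 6,000 runs per cell (8,000 for 30 v 20 at r = 0.5 and 0.67).

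| Sizes | r = 0.5 | 0.67 | 1 | 1.5 | 2 |
|---|---|---|---|---|---|
| 60 v 20 | 0.95% | 2.0% | 5.3% | 10.3% | 15.5% |
| 30 v 20 | 3.1% | 3.3% | 5.3% | 7.4% | 8.8% |
| 20 v 20 | as r = 2 | as r = 1.5 | 4.9% | 5.8% | 5.9% |
| Welch, no pretest, 60 v 20 | 5.3% | 4.9% | 5.0% | 5.0% | 5.3% |

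Wilcoxon alone at 60 v 20 gives 7.4% and 10.2% at r = 1.5 and 2, and 2.8% and 2.1% at r = 0.67 and 0.5.

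**Step 3: what the pretest itself contributes.** With equal variances at 60 v 20 the two-stage rule gives 5.3% (normal), 5.3% (gamma), 5.2% (t with 5 df), and 5.7% and 4.6% (log-normal, log-SD 0.5 and 1). It adds under 1 point. With unequal variances and skewed (gamma) data, keeping the pretest and only replacing pooled t by Welch still gives 9.8% and 13.1% at r = 1.5 and 2, because Wilcoxon is then used in about 85% of runs. Welch without the pretest stays between 4.8% and 5.7%.

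**Step 4: the ANOVA rule.** With four groups of 20/60/30/30: 5.2% with equal SDs; 8.3% and 12.3% if the 20-child group has 1.5 or 2 times the SD; 2.2% if the 60-child group has twice the SD. With all eight cohorts as groups: 4.9% with equal SDs; about 9% and 13% if the infected groups have 1.5 or 2 times the SD; 3.5% if the vaccinated groups have twice the SD. The plan does not define the ANOVA groups, so both layouts are assumptions.

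**Step 5: carry-over to the FDR.** For an assumed 20 independent true-null responses at 60 v 20, pooled t followed by Benjamini-Hochberg at 0.05 gives an actual FDR of 23.5% at r = 1.5 and 44% at r = 2. Welch gives 5.6% and 5.2%.

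**Step 6: switching between visits.** Pretest run at each of three visits, assumed within-child correlation 0.5, 60 v 20. The chosen test is not the same at all three visits for 27% of responses with normal data, 55% to 71% with mild skew (log-normal log-SD 0.2 to 0.3, gamma shape 10), 36% with gamma shape 4, and 6% and 0% with strong skew (log-SD 0.5 and 1).

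**The case against.** Several stronger readings are tempting and should be set aside.

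- A reader might infer that the plan pushes error above 5%. The documents give no variances, so the direction is unknown. The same rule is conservative when the larger group is more variable.
- A reader might blame the pretest for the inflation. With equal variances it adds under 1 point. The cause is unequal variance combined with unequal size; the pretest does not detect it and, with skewed data, sends most comparisons to a rank test that is also affected.
- A reader might say that the plan chose the pooled t-test. Section 11.4 does not say which version. If Welch was meant, the normal-data inflation largely disappears; the skewed-data problem in Step 3 does not.
- A reader might treat 60 v 20 as typical. It arises in one age cohort of four. Cohort 2A is recruited as 35 younger and 25 older children; analysed that way against 20 infected children, the rate at r = 2 is 9.2% and 6.9%.
- Switching by visit is possible, not specified. The phrase about time points attaches to the comparison, and the unit of the pretest is unstated.

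It is also fair to say that 0.05 is an FDR level and not a promised per-test error, that Section 11.2 presents the study as hypothesis-generating, and that linear and mixed models with no stated pretest are planned as well. The ANOVA belongs to the revaccination visits, where all children receive the same vaccine and are sampled on the same days after it, so spread due to time since illness onset explains less there.

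These points limit the size of the concern. What stands is that Benjamini-Hochberg needs valid p-values, that nothing in the plan protects them against unequal spread, and that a test which does so costs almost nothing.

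**Conclusion.** The concern holds in a limited form. Section 11.4 makes the test depend on a pretest that ignores spread, leaves the t-test version open, and names an F-test that usually assumes equal variances, with group sizes from 20 to 60.

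If the t-test is pooled, the false-positive rate is about 1% to 15% at 60 v 20, about 3% to 9% at 30 v 20, and near 5% at 20 v 20, for SD ratios of 0.5 to 2. Those ratios, the pretest level and its unit are assumptions. The documents do not support a claim that differences will be declared too often; they support only that the error rate is uncontrolled in either direction and that the stated FDR could fail. Inconsistent tests across visits are a real possibility under mild skew, and rare under strong skew.

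**What to change.** Remove the normality pretest from Section 11.4. Name the Welch t-test for two-group comparisons and Welch ANOVA for several groups, for each response at all visits, and define the ANOVA groups.

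Fix the scale of each response in advance, for example log for titres and other positive, right-skewed measures. A blanket log transformation with an open offset is not advisable. With an assumed 40% zeros at 20 v 20, the power of Welch on the log scale ran from 8% to 30% as the offset went from 0.001 to 1, against 18% for Wilcoxon. For responses with many zeros, either fix the offset beforehand or name the rank test as primary, accepting that it compares distributions and not means.

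Report rank tests for the remaining responses as a sensitivity analysis.

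The cost is wording in the analysis plan and about 1 to 2 points of power at 60 v 20 if variances are in fact equal: about 80% for Welch against 82% for pooled t at a difference of 0.75 SD.

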2.2 Scientific Rationale

This protocol is a population-based study that will address the hypothesis that vaccination and infection differentially drive both the CD4 T cell and B cell immunity. Recent data in the literature [3,4,28], and our own preliminary data suggest that initial encounters with influenza have a long lasting effect on both CD4 T cell and B cell mediated immunity. This protocol will address how early immunity against influenza virus is primed by vaccination versus infection and whether this differentially poises subsequent immune responses on re-challenge with influenza vaccination. We will specifically test whether the more robust pro-inflammatory response initiated on first exposure to a natural influenza infection promotes imprinting of both CD4 T cell and B cell responses, influencing long term specificity and functionality. We also will examine the effects of age and exposure on the immune response that develops following influenza vaccination. To do this, we will first examine whether early exposure to a live viral infection compared to vaccination leads to a distinct phenotype and specificity in both the B cell and CD4 T cell compartments. Subsequently, we will determine whether the CD4 T cell repertoire is remodeled over time by examining CD4 T cell specificity, cytokine production, and expression of markers and transcriptional factors associated with a negative regulatory CD4 T cell phenotype in children of different ages versus adults.

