3.2 Outcome Measures

3.2.1 Primary Outcome Measures

- Assess the frequency and functional potential of CD4 T cell responses on a single cell level using full spectrum flow cytometry following either infection or inactivated influenza vaccine administration, with stratification by age and exposure history

[figure not shown]

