Here y_{kit} represents the k th response variable measured from the i th subject at the t th time point; α_k is the overall mean value of y_{kit} ; $G(i)$ is a binary variable which equals 0 if the i th subject is vaccinated with IIV and 1 otherwise; β_{1k} is a linear coefficient that quantifies the magnitude of the group-effect; β_{2k} are linear coefficients for potentially confounding clinical variables listed above; γ_{kt} is a random effect term that quantifies the time effects; and $\dot{\mathbf{0}}_{kit}$ represents independent measurement errors. Likelihood ratio test will be used to test $H_0 : \beta_k = 0$ against $H_1 : \beta_k \neq 0$.

In case of high-dimensional data in different scales, standardization will be applied before model fitting and variable selection. Variable selection approaches using AIC or BIC criteria will be used to select the significant predictors. Penalized-based variable selection procedures such as LASSO [39] or SCAD [40,41] may be used to overcome the drawbacks of ad-hoc methods of stepwise, best subset selection, etc. post-hoc.

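### The planned analysis does not carry the primary outcome's age stratification through: the re-challenge ANOVA has undefined groups, and the models have no arm-by-age-cohort term.

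*Combined protocol and SAP*

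**What the plan says.** Section 3.2.1 defines the primary outcome as CD4 T cell frequency and function "following either infection or inactivated influenza vaccine administration, with stratification by age and exposure history". Section 2.2 adds the re-challenge question: whether early immunity is primed differently by vaccination and by infection, and "whether this differentially poises subsequent immune responses on re-challenge with influenza vaccination". Section 5 sets out two arms by four age cohorts. The vaccination arm (A) has 20, 60, 30 and 30 children and the infection arm (B) has 20 in each cohort, 220 in all.

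Section 11.4 plans three kinds of analysis.

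- **Season 1:** two-sample t-tests or Wilcoxon rank-sum tests, which "will be used to detect significant mean difference between the children of different ages and flu exposures at each time point".
- **Re-vaccination seasons:** a one-way ANOVA or Kruskal-Wallis test "to detect significant group differences at each time point".
- **Models:** general linear models of change from baseline that control for age among other confounders, and mixed model (0.1). In model (0.1), G(i) "is a binary variable which equals 0 if the i th subject is vaccinated with IIV and 1 otherwise", and its coefficient is "a linear coefficient that quantifies the magnitude of the group-effect". The covariates enter additively.

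The Benjamini-Hochberg adjustment is justified by the number of response variables. Section 11.2 gives no effect size, SD or power.

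**The concern.** The outcome asks for infection versus vaccination within age strata. An omnibus test over unspecified groups does not answer that, and its meaning changes with the reading:

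- Over the eight cells, it mixes age with arm.
- Over the four age cohorts, it does not test arm.
- Over the two arms, it takes no account of the different age mix in A and B.

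A model with a single arm coefficient returns one average across cohorts. It cannot show whether the arm effect differs by age, or whether it sits mainly in the infants, where section 2.2 looks for the primary response. What is at stake is a re-challenge result that cannot be attributed to arm, and a cohort-specific effect that is averaged away. If the contrasts are left open, they could also be chosen once data are in view, and section 11.3 says assay results will be reviewed as they become available.

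**Working it through.** The plan states no power or effect size, so there is no figure to reproduce beyond the total: 20 + 60 + 30 + 30 + 4 × 20 = 220.

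**1. Which planned analysis gives arm within age cohort?**

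| Analysis in section 11.4 | Arm within cohort? |
|---|---|
| Season 1 two-sample tests | Possible (1A v 1B to 4A v 4B), but pairs not named; age v age or pooled A v B fit the wording equally well |
| Seasons 2 and 3 one-way ANOVA or Kruskal-Wallis | No; groups undefined, no follow-up contrast |
| General linear models | Arm adjusted for age; no interaction stated |
| Model (0.1) | One arm coefficient, additive covariates; no interaction |

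**2. Inputs for the illustration.** Cell sizes are from section 5. The assumptions are SD 1, two-sided alpha 0.05 without FDR adjustment, and all 220 children measured. Error df = 220 − 8 = 212. Power is from the noncentral F distribution.

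**3. Eight-cell ANOVA when only age matters.** Cohort 1 (40 children) is shifted by 0.8 SD and arm has no effect.

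Noncentrality = (40 × 180 / 220) × 0.8² = 20.9 on 7 and 212 df, giving 93% rejection.

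A 4,000-trial simulation with cohort means of 0, 0.3, 0.6 and 0.9 SD and no arm effect also gave 93% for the ANOVA. In the same trials an additive arm term rejected in 5.2% and the arm-by-cohort interaction in 4.7%.

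**4. Dilution by a single arm coefficient.** In an arm + cohort model, each cohort's arm difference has weight nA·nB/(nA + nB):

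- cohort 1: 20 × 20 / 40 = 10
- cohort 2: 60 × 20 / 80 = 15
- cohorts 3 and 4: 30 × 20 / 50 = 12 each
- total: 49

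Take an arm effect of 0.8 SD in cohort 1 only:

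- averaged coefficient = 0.8 × 10 / 49 = 0.163 SD; noncentrality = 0.163² × 49 = 1.31; power 21%
- cohort 1 contrast: noncentrality = 0.8² × 10 = 6.4; power 71%
- 3-df interaction: noncentrality = 6.4 − 1.31 = 5.09; power 44%

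The simulation gave 20%, 69% and 43%. Its 69% comes from a t-test that uses cohort 1 alone to estimate the error. With arm effects of opposite sign (+0.8, +0.8, −0.83, −0.83 SD), the additive arm term rejected in 3.6% of trials and the interaction in about 100%.

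**5. Constant arm effect, for comparison.** At 0.4 SD the cohort-adjusted 1-df arm contrast has noncentrality 0.4² × 49 = 7.84 and 80% power. The eight-cell ANOVA has 49%. At 0.5 SD the figures are 94% and 72%.

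**6. What the within-cohort contrasts can detect.** Differences found with 80% power by t-test are 0.91 SD in cohort 1, 0.73 SD in cohort 2, and 0.83 SD in cohorts 3 and 4.

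**The case against.** Much of the case on the other side stands, and it limits the point.

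- **A reader might infer that no planned test gives the age-stratified contrast.** The documents do not support that. The season 1 two-sample tests cover different ages and exposures and can be run cohort by cohort, and season 1 is where the direct response to infection or vaccination is measured. The gap there is unnamed pairs.
- **A reader might infer from step 5 that a general arm effect is tested with much less power than the data allow.** That holds only if the eight-cell ANOVA were the sole test of arm. The planned models also test arm with age controlled. An additive arm + cohort contrast at one time point has about 80% power at 0.4 SD. Group may also mean arm, since model (0.1) uses the word that way; the ANOVA would then have two groups and 81% power at 0.4 SD.
- **A reader might infer that the age mix biases the arm comparison.** If cohort 1 were 1 SD lower, an unadjusted A v B difference would be off by (20/80 − 20/140) × (−1) = −0.11 SD. This does not carry over to models that control for age.
- **Age-cohort differences are partly the target.** The cohorts stand in for exposure history, so an ANOVA that responds to age is not simply wrong. It still does not separate age from arm.
- **The full sample is optimistic.** Infection enrolment is up to 80, blood is drawn if able, and about two-thirds are expected in the optional season. At two-thirds, the adjusted arm contrast at 0.4 SD has 62% power.
- **The study looks for trends** (section 11.2). That lowers the severity. Section 11.1 nonetheless states a hypothesis to be tested, and section 11.4 sets an FDR level, so the contrasts need definition.

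**Conclusion.** The point holds as a should-fix. For the re-challenge seasons, no written test isolates infection versus vaccination within an age cohort, and neither the general linear models nor model (0.1) can, as written, show whether the arm effect varies by age. For season 1 the contrast is available but not specified. Under the stated assumptions, an effect confined to cohort 1 has about 21% power through the single coefficient and about 71% through its own contrast, and the eight-cell ANOVA can reject 93% of the time on age alone. The sizes are illustrative, because the documents give no SD. The structural gap does not depend on them.

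It is also tempting to call the cohort 1 contrast a clean test of first exposure. The documents do not support that. Section 5.2 lets vaccine failures enter the B cohorts, so 1B may include vaccinated infants. Section 5.1 admits 1B from 3 months and 1A from 6 months. The first post-vaccination sample in 1A follows the second dose (section 2.2).

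**What to change.** In section 11.4:

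1. At each time point in every season, fit arm + age cohort + arm × cohort in place of the one-way ANOVA. Name a cohort-stratified rank test, such as van Elteren's, for non-normal data.
2. Report the four within-cohort infection-versus-vaccination contrasts, the cohort-adjusted overall arm contrast and the 3-df interaction. If the season 1 two-sample tests stay, name their pairs as 1A v 1B to 4A v 4B.
3. Add cohort and G × cohort to model (0.1).
4. Include these contrasts in the Benjamini-Hochberg family.
5. Describe the cohort 1 contrast as the one closest to first exposure, with the caveats on prior vaccination and age range in 1B.

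This is a change of wording that uses variables already collected. It costs 3 df for the interaction and enlarges the multiplicity family. Power for the interaction stays modest (44% in the cohort 1 example), so a non-significant interaction should not be read as evidence of the same effect at every age.
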